5.2 Pre-Treatment Criteria

Please note: TSH results are not required to be available prior to dosing.

5.2.1 Targeted Therapy Lead-in Phase, Day 1 Week 1

- Physical examination including vital signs and performance status
- Labs values do not need to re-meet eligibility criteria on Week 1, Day 1
- Comprehensive metabolic panel including liver function tests
- Complete blood count (CBC w/diff, plts)
- ECG (in BRAF^{V600} mutant cohort only)

5.2.2 Combination Targeted Therapy Plus Phase, Day 1 Week 3 and Day 22 Week 6

- Physical exam including vital signs and performance status
- Comprehensive metabolic panel including liver function tests
- Complete blood count (CBC w/diff, plts)
- ECG (in BRAF^{V600} mutant cohort)
- Serum pregnancy test (Day 1 Week 3 for women of childbearing potential only)

5.2.3 Single-agent pembrolizumab Phase, Week 9

- Physical examination including vital signs and performance status
- Dermatology Exam
- Ophthalmology Exam
- Echo/MUGA
- Comprehensive metabolic panel including liver function tests
- Complete blood count (CBC w/ diff, plts)
- Serum pregnant test (for women of childbearing potential only)

5.2.4 Single-agent pembrolizumab Phase, Week 12 onwards

- Physical examination including vital signs and performance status
- Comprehensive metabolic panel including liver function tests
- Complete blood count (CBC w/ diff, plts)
- Serum pregnant test (Week 5 and 21 only and for women of childbearing potential only)

CONFIDENTIAL

This document is confidential. Do not disclose or use except as authorized.

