10. STUDY CALENDAR

Baseline evaluations are to be conducted within 2-weeks prior to start of protocol therapy. Scans must be done \leq 4 weeks prior to the start of therapy. All assessments must be performed prior to administration of any study medication. On days when TSH is required, TSH is not required to be resulted prior to administration of study medication. All study assessments and medications should be administered within \pm 3 days of the protocol-specified date, unless otherwise noted. Laboratory values do not need to re-meet eligibility criteria on Week 1, Day 1.

CONFIDENTIAL

This document is confidential. Do not disclose or use except as authorized.

BRAF ^j	X			X	X	X	X	X	X	X	X	X ⁱ	
PBMC ^k	X			X		X	(X)						
Tumor Biopsies ^k	X			X		X	(X)						
Rash Prophylaxis ^q		X ^q	X ^q	X ^q	X ^q								

- a. MAPK targeted therapy (MTT): In cohort 1, participants will be treated with the combination of dabrafenib and trametinib. In cohort 2, participants will be treated with trametinib. MTT will commence week 1, day 1 and be given continuously (except in the setting of toxicity) for two weeks in the lead-in phase and then 6-weeks in combination with pembrolizumab. Only if patients develop symptomatic or radiographic progression at anytime AFTER initial MTT-phase completion, then MTT may be resumed at a previously tolerated dose in combination with ongoing pembrolizumab.
- b. Participants will be seen on day 1 (+/-3 days) of week 1, week 3, and then every three weeks while remaining on therapy. If treatment is discontinued for a reason other than disease progression, study discontinuation, or withdrawal of consent, patients will be seen every 12 weeks (+/- 2 weeks).
- c. Dermatological examination done at screening, and within 1 week prior to dosing on week 9. A full-body skin examination and removal of pre-existing calluses and keratotic skin is recommended prior to initiation of study treatment (See Table 6-4).
- d. Ophthalmological examination done at screening and within 1 week prior to treatment on week 9. For Grade 2 visual changes or greater, an exam must occur within 24 hours of onset (or study team knowledge of the event). Consult ophthalmologist any time when patient reports visual disturbance. If there is visual loss or significant visual changes, consult ophthalmologist immediately (within 24 hours)
- e. Single EKG will be collected at screening and repeated on day 1 of weeks 3 and 6 in cohort 1.

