- f. Albumin, alkaline phosphatase, total bilirubin, BUN, creatinine, calcium, chloride, glucose, HCO₃, LDH, phosphorus, potassium, total protein, SGOT [AST], SGPT [ALT], sodium. TSH will be performed at baseline, week 3 and then every 6 weeks.
- g. Radiographic imaging will be performed within 4 weeks of lead-in therapy commencement, within 1 week prior to Week 9, every six weeks thereafter (within 1 week prior to W15, W21, W27) until week 27, and then every 12 weeks (+/- 2 weeks) through 48 weeks of pembrolizumab therapy. Additionally, following initial disease progression, if a participant is treated beyond progression, tumor assessments must be repeated ≥ 4 weeks after initial disease progression in order to confirm disease progression. The tumor assessment must not be repeated any sooner than 4 weeks after initial disease progression.
- h. Serum pregnancy test (women of childbearing potential).
- i. Ejection fraction measurement done at screening and within 1 week prior to dosing on week 9. The same modality (ECHO or MUGA) should be used at baseline and at follow-up; should be performed with increased frequency if clinically indicated.

CONFIDENTIAL

This document is confidential. Do not disclose or use except as authorized.

- j. Correlative blood analysis will be performed prior to MTT, prior to pembrolizumab therapy initiation, prior to every pembrolizumab dose through week 27, prior to every other pembrolizumab dose after week 27 (week 33, week 39, etc.), and at time of disease progression. BRAF samples will be collected in 1-10 mL green sodium heparin and 1-10 mL red top serum tubes
- k. Tumor biopsies and PBMC blood analysis will be performed pretreatment, prior to pembrolizumab therapy initiation (up to 5 days prior), at the conclusion of combined targeted therapy plus pembrolizumab therapy (up to 5 days prior), and then at the time of disease progression. PBMC samples will be collected in 2-8 mL blue tiger top CPT tubes.
- l. Pembrolizumab will be administered at a dose of 200 mg IV every three weeks.

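### Section 5.2.4 starts at Week 12 but sets one of its two pregnancy tests at Week 5, which is not a scheduled visit; Week 15 was probably meant

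*Combined protocol and SAP*

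**What the plan says.** Section 5.2 sets the pre-treatment checks phase by phase. The pregnancy test appears in three places:

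- Section 5.2.2 (combination phase, visits at Weeks 3 and 6): "Serum pregnancy test (Day 1 Week 3 for women of childbearing potential only".
- Section 5.2.3 (Week 9): "Serum pregnant test (for women of childbearing potential only".
- Section 5.2.4, headed "5.2.4 Single-agent pembrolizumab Phase, Week 12 onwards": "Serum pregnant test (Week 5 and 21 only and for women of childbearing potential only".

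The notes to the study calendar (Section 10) fix the visit pattern. Note b says: "Participants will be seen on day 1 (+/-3 days) of week 1, week 3, and then every three weeks while remaining on therapy". Note h confirms that the calendar has a pregnancy-test entry but gives no weeks: "Serum pregnancy test (women of childbearing potential". Two other assessments have their weeks spelled out: thyroid function in note f ("TSH will be performed at baseline, week 3 and then every 6 weeks") and imaging in note g, with a scan before Week 9 and then "every six weeks thereafter (within 1 week prior to W15, W21, W27) until week 27".

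**The concern.** A list that applies from Week 12 cannot order something at Week 5. A coordinator who turns to Section 5.2.4 when a participant reaches Week 12 finds two test weeks, one of which has already passed and never had a visit attached to it.

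This is an operative safety instruction to be met before dosing, not background text. Section 5.8 warns of possible fetal harm from pembrolizumab. Planned targeted therapy is over by Week 9, but note a of the calendar allows it to be resumed on progression alongside pembrolizumab, and Section 3.2.10 describes both targeted agents as potentially teratogenic. If the line leads a site to do no test between Weeks 9 and 21, a pregnancy could go undetected for longer than was probably intended.

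**Working it through.** No design figure is involved. The check is schedule arithmetic.

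**1. Visit weeks.** Under note b, visits fall at Week 1, Week 3 and then every three weeks: 1, 3, 6, 9, 12, 15, 18, 21, 24, 27, 30. Week 21 is in the list and lies at or after Week 12. Week 5 is not in the list, and 12 − 5 = 7 weeks before the phase starts.

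**2. Visit window.** Day 1 of Week 6 is study day 5 × 7 + 1 = 36. With ±3 days, that visit spans days 33 to 39. Week 5 is days 29 to 35, so an early Week 6 visit can fall on a Week 5 date. It remains the Week 6 visit under Section 5.2.2, which orders the pregnancy test at Week 3 only.

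**3. Other ways of counting weeks.** Suppose the line counts from another starting point:

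| Count starts at | Start visit called | Week 5 becomes study week | Week 21 becomes study week |
|---|---|---|---|
| First pembrolizumab (Week 3) | week 1 | 7 | 23 |
| First pembrolizumab (Week 3) | week 0 | 8 | 24 |
| Single-agent phase (Week 9) | week 1 | 13 | 29 |
| Single-agent phase (Week 9) | week 0 | 14 | 30 |

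Weeks 24 and 30 are visits, so for the second test the answer depends on the convention. For the first test it does not: none of 7, 8, 13 and 14 is a visit week.

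**4. Resulting test intervals.** Doses are counted from each test up to, but not including, the next test visit.

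| Reading | Test weeks | Gaps (weeks) | Pembrolizumab doses per gap |
|---|---|---|---|
| Workable scheduled visits only | 3, 9, 21 | 6, 12 | 2 (Weeks 3, 6); 4 (Weeks 9, 12, 15, 18) |
| Week 15 in place of Week 5 | 3, 9, 15, 21 | 6, 6, 6 | 2, 2, 2 |

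If a site instead arranged an unscheduled test at Week 5, the tests would be at Weeks 3, 5, 9 and 21, with gaps of 2, 4 and 12 weeks. The 12-week gap remains.

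**5. Why Week 15.** It differs from Week 5 by one digit, is a scheduled visit, lies inside the phase, and makes the series even. Thyroid testing under note f runs at Weeks 3, 9, 15, 21 and 27, and imaging under note g is tied to Weeks 9, 15, 21 and 27. These are separate assessments, so they make Week 15 plausible without proving it.

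**The case against.** The strongest reply is that the deciding row cannot be seen. The calendar is the natural per-visit schedule and has a pregnancy-test entry, but that row is missing from the text available because of how the PDF was read. If it shows Week 15, sites already have a valid visit and what remains is a dropped digit in Section 5.2.4. A character lost in extraction cannot be fully excluded either. This stands. It limits what can be said about consequences and makes checking the source the first step. It does not make the printed line workable.

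A second reply is that other safeguards matter more. Section 5.8 requires contraception through 120 days after the last dose. Section 3.1.9 requires a woman who is or may be pregnant to tell her physician at once, and bars entry where compliance with contraception is in doubt. Section 5.2 orders no test after Week 21 although pembrolizumab may run for up to two years, so frequent testing is not what the plan chiefly relies on. This also stands, and it keeps the point minor.

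A reader might infer that the whole line is unusable. It is not: Week 21 is sound. A reader might also infer that a planned test has been lost, or that text and calendar conflict. The documents support neither. Read literally, the line orders an off-schedule test rather than deleting one, a lost test follows only if Week 15 was intended, and nothing can be said about what the calendar row shows.

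**Conclusion.** The inconsistency is real. The Week 5 half of the pregnancy-test line in Section 5.2.4 lies outside the phase it governs and matches no scheduled visit under any week count tried. For a site working from Section 5.2 alone, or if the calendar repeats the slip, the interval between usable tests is 12 weeks and four doses, against 6 weeks and two doses with a Week 15 test.

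That Week 15 was meant is a probable inference and rests on the pattern of the schedule. The size is minor: only women of childbearing potential are affected (the documents do not give their number), and nothing changes in the primary endpoint, the sample size or the analysis.

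**What to change.** Check the line in Section 5.2.4 against the source page and against the pregnancy-test row of the Section 10 calendar. If the calendar shows Week 15, change Week 5 to Week 15 in Section 5.2.4. If the calendar also shows Week 5, correct both to Week 15. If it shows another visit week inside the phase, make Section 5.2.4 match it.

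The cost is one row check and one digit, or two if the slip is repeated. A Week 15 test adds no visit and no separate blood draw, because Section 5.2.4 already requires a metabolic panel and blood count then. The only addition is one assay for the women concerned.

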5.3 Agent Administration

5.3.1 Pembrolizumab

- Intravenous
- 200 mg IV every three weeks, to commence after 2-week lead-in Phase of MTT
- Missed doses held for toxicity will not be made up.
- On days when this treatment is given, it should be done so after trametinib dosing, during the concurrent MTT phase

5.3.2 Dabrafenib (BRAF^{V600} mutant cohort only)

- Oral
- 150 mg PO BID, to be taken every twelve hours; can be taken together with trametinib
- Dabrafenib should be taken on an empty stomach at least one hour before or two hours after a meal; water is permitted during this fasting period.
- Missed or vomited doses will not be made up.
- If a dose is missed, it can be taken up to 6 hours prior to the next dose to maintain the twice daily regimen.
- The drug cannot be crushed, chewed, or dissolved
- In the BRAF mutant cohort, this should be taken before trametinib
- The medication diary and pill bottles will be returned to clinic staff at the end of the lead in period and at the end of each three week cycle.

5.3.3 Trametinib (BRAF^{V600} mutant or BRAF^{V600} wild-type cohorts)

- Oral
- 2 mg PO daily; can be taken together with dabrafenib
- Trametinib should be taken on an empty stomach at least one hour before or two hours after a meal; water is permitted during this fasting period.
- Missed or vomited doses will not be made up.
- If a dose is missed, it can be taken up to 12 hours after scheduled dose time.
- The drug cannot be crushed, chewed, or dissolved
- In the BRAF^{V600} mutant cohort, this should be taken after dabrafenib.
- On days when pembrolizumab is given to patients in either the BRAF^{V600} mutant or BRAF^{V600} wild-type cohorts, this should be taken before pembrolizumab therapy.
- The medication diary and pill bottles will be returned to clinic staff at the end of the lead in period and at the end of each three week cycle.

CONFIDENTIAL

This document is confidential. Do not disclose or use except as authorized.

5.3.4 Other Modality(ies) or Procedures

Palliative stereotactic radiation or surgery may be performed during study participation. Dabrafenib and/or trametinib must be held for two days before and two days after surgery or the commencement and completion of stereotactic radiation. Pembrolizumab dosing must be held for two weeks before and after surgery or the commencement and completion of stereotactic radiation. If palliative, standard fractionated, external beam radiation is indicated, then a discussion with the investigator, the principal investigator, and Merck will be held to discuss whether the patient should be allowed to remain on trial, and if so, if and for how long dabrafenib, trametinib, and/or pembrolizumab should be held.

5.4 General Concomitant Medication and Supportive Care Guidelines

5.4.1 Acceptable Concomitant Medications

All treatments (outside of the medications or vaccinations specifically prohibited in the exclusion and in Section 5.4.2) that the investigator considers necessary for a subject's welfare may be administered at the discretion of the investigator in keeping with the community standards of medical care. All concomitant medication will be recorded on the case report form (CRF) including all prescription, over-the-counter (OTC), herbal supplements, and IV medications and fluids. If changes occur during the trial period, documentation of drug dosage, frequency, route, and date must also be included on the CRF.

All concomitant medications received within 28 days before the first dose of trial treatment and 30 days after the last dose of trial treatment should be recorded. Concomitant medications administered after 30 days after the last dose of trial treatment should only be recorded for SAEs and ECIs as defined in Section 7.

5.4.2 Prohibited Concomitant Medications

Subjects are prohibited from receiving the following therapies during the Screening and Treatment Phase (including retreatment for post-complete response relapse) of this trial:

- Antineoplastic systemic chemotherapy or biological therapy
- Immunotherapy not specified in this protocol
- Chemotherapy not specified in this protocol
- Investigational agents other than pembrolizumab not specified in this protocol

CONFIDENTIAL

This document is confidential. Do not disclose or use except as authorized.

- Live vaccines within 30 days prior to the first dose of trial treatment and while participating in the trial. Examples of live vaccines include, but are not limited to, the following: measles, mumps, rubella, varicella/zoster, yellow fever, rabies, BCG, and typhoid vaccine.
- Systemic glucocorticoids for any purpose other than to modulate symptoms from an event of clinical interest of suspected immunologic etiology. The use of physiologic doses of corticosteroids may be approved after consultation with the Overall PI.
- Strong inhibitors/inducers of selected CYP450 isoenzymes. Dabrafenib mesylate is a substrate for CYP 3A4, 2C8, p-glycoprotein (Pgp), and breast carcinoma resistance protein (Bcrp). These enzymes and transporters are prohibited for eligibility and during the study. Because the lists of these agents are constantly changing, it is important to regularly consult a frequently-updated list such as <http://medicine.iupui.edu/clinpharm/ddis/table.aspx>; medical reference texts such as the Physicians' Desk Reference may also provide this information.
- Concomitant medications should be reviewed for the potential risk of inducing nephrotoxicity and, if so, should be modified if clinically possible (See 6.2.6)

If there is a clinical indication for one of these or other medications or vaccinations specifically prohibited during the trial, discontinuation from trial therapy or vaccination may be required. The investigator should discuss any questions regarding this with the Merck Clinical team. The final decision on any supportive therapy or vaccination rests with the subject's primary investigator. Subjects may receive other medications that the investigator deems to be medically necessary.

The Exclusion Criteria describes other medications that are prohibited in this trial.

There are no prohibited therapies during the Post-Treatment Follow-up Phase.

CONFIDENTIAL

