6.2.2 Dabrafenib + Trametinib Dose Modification Requirements for **Pyrexia**

- Pyrexia is defined as a body temperature equal to or above 38.5° Celsius or 101.3° Fahrenheit
- Pyrexia is an adverse event associated with dabrafenib. In a minority of cases, pyrexia was accompanied by symptoms such as severe chills/rigors, dehydration, hypotension, dizziness or weakness and required hospitalization.
- Subjects should be instructed on the importance of immediately reporting febrile episodes.
- Pyrexia accompanied by hypotension, dehydration, renal insufficiency and/or severe (grade ≥3) rigors/chills in the absence of an obvious infectious cause should be reported as an SAE.

CONFIDENTIAL

This document is confidential. Do not disclose or use except as authorized.

Table 6-2: Dabrafenib + Trametinib dose Modification and Management Requirements for Pyrexia

Event	Management Guideline	Dose Modification

Work up:
 
 • Clinical evaluation for infection and hypersensitivity, especially if pyrexia is complicated by rigors, severe chills, dehydration, etc. • Laboratory work-up (recommend include full-blood-count, electrolytes, creatinine, BUN, CRP, liver-function tests, blood and urine culture). 
Management:
 
 • Anti-pyretic treatment should be started immediately at the first occurrence. Anti-pyretic treatment may include acetaminophen (paracetamol), ibuprofen, or suitable anti-pyretic medication per institutional standards. • Oral hydration is encouraged in subjects without evidence of dehydration. Intravenous hydration is recommended if pyrexia is complicated by dehydration/hypotension. • In subject experiencing pyrexia complicated by rigors, severe chills, etc., which cannot be controlled with anti-pyretic medication, recommend oral corticosteroids be started. • Prophylactic anti-pyretic treatment is recommended after the 2nd event. 		

1st Event:
	
 • Clinical evaluation for infection and hypersensitivity • Laboratory work-up • Hydration as required • Administer anti-pyretic treatment if clinically indicated and continue prophylactic treatment 	
 • Interrupt dabrafenib. • Continue trametinib. • Upon recovery to baseline, restart dabrafenib at the same dose level. If fever was associated with dehydration or hypotension, reduce dabrafenib by one dose level.

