
2nd Event
	
 • Clinical evaluation for infection and hypersensitivity • Laboratory work-up • Hydration as required • Within 3 days of onset of pyrexia: 
 – Optimize anti-pyretic therapy. – Consider oral corticosteroids (i.e., prednisone 10 mg) for at least 5 days or as clinically indicated. 	
 • Interrupt dabrafenib. • Continue trametinib. • Upon recovery to baseline, restart dabrafenib at the same dose level. If fever was associated with dehydration or hypotension, reduce dabrafenib by one dose level.

CONFIDENTIAL

This document is confidential. Do not disclose or use except as authorized.

Table 6-2: Dabrafenib + Trametinib dose Modification and Management Requirements for Pyrexia

Event	Management Guideline	Dose Modification
Subsequent Events:	
 • Clinical evaluation for infection and hypersensitivity • Laboratory work-up • Hydration as required • Blood sample for cytokine analysis • Within 3 days of onset of pyrexia: 
 – Optimize oral corticosteroid dose as clinically indicated for recalcitrant pyrexia. – If corticosteroids have been tapered and pyrexia recurs, restart steroids. – If corticosteroids cannot be tapered, consult medical monitor. 	
 • Interrupt dabrafenib. • Continue trametinib. • Once pyrexia resolves to baseline, restart dabrafenib reduced by one dose level.^h • If dabrafenib must be reduced to <75 mg BID, permanently discontinue dabrafenib.

^h Dabrafenib should be reduced by one dose level after three episodes of pyrexia which cannot be managed by best supportive care and increasing doses of oral steroids. Escalation of dabrafenib is allowed if no episode of pyrexia is observed in the 4 weeks subsequent to dose reduction.
		

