
Grade ≥3
 
 • 	
 • Use moderate strength topical steroids PLUS oral methyl-prednisolone dose pack.² • Consult dermatologist. 	
 • Interrupt study treatment until rash recovers to ≤ grade 1. • Restart with study treatment reduced by one dose level.^{3,4} • If no recovery to ≤ grade 2 within 21 days, permanently discontinue study treatment.

1. Rash prophylaxis is recommended for the first 6 weeks of study treatment. 2. Moderate-strength topical steroids: Hydrocortisone 2.5% cream or fluticasone propionate 0.5% cream. 3. Approval of overall PI is required to restart study treatment after >21 days of interruption. 4. Study treatment may be escalated to previous dose level if no rash is evident 4 weeks after restarting study treatment.
		

CONFIDENTIAL

This document is confidential. Do not disclose or use except as authorized.

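### Section 5.4.2 limits systemic steroids to suspected immune events or approved physiologic doses, while the pyrexia and rash tables call for them for targeted-therapy toxicity, with no cross-reference

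*Combined protocol and SAP*

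**What the plan says.** **The restriction.** Section 5.4.2 lists, among therapies not allowed in the screening and treatment phase, "Systemic glucocorticoids for any purpose other than to modulate symptoms from an event of clinical interest of suspected immunologic etiology". The same bullet adds: "The use of physiologic doses of corticosteroids may be approved after consultation with the Overall PI". If a prohibited medication is clinically indicated, "discontinuation from trial therapy or vaccination may be required". The paragraph then sends questions to the pembrolizumab supplier's clinical team and states: "The final decision on any supportive therapy or vaccination rests with the subject's primary investigator".

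**The pyrexia table.** Section 6.2.2 attributes the event to targeted therapy: "Pyrexia is an adverse event associated with dabrafenib". Under general management, for fever complicated by rigors, severe chills and the like "which cannot be controlled with anti-pyretic medication, recommend oral corticosteroids be started". At the second event sites are to consider oral corticosteroids. For later events: "Optimize oral corticosteroid dose as clinically indicated for recalcitrant pyrexia", with steroids restarted if fever returns after a taper. Footnote h makes a dabrafenib reduction depend on three episodes that neither best supportive care nor escalating oral steroids could manage.

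**The rash table.** Section 6.2.3 links rash to trametinib, dabrafenib or both. For grade 3 or higher, Table 6-3 says: "Use moderate strength topical steroids PLUS oral methyl-prednisolone dose pack".

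Neither of these Section 6.2 tables mentions 5.4.2, and 5.4.2 makes no exception for them.

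**The concern.** A site treating fever or severe rash that it attributes to dabrafenib or trametinib finds two instructions. One part of the protocol tells it to give, or consider, an oral steroid. Another classes that steroid as prohibited for such a purpose and says that needing it may mean coming off trial therapy. Sites could resolve this differently: give the steroid and continue, give it and record a deviation, ask the Overall PI first, withhold it, or stop therapy. What is at stake is consistent management of a recognised toxicity and consistent handling of discontinuation. Steroid exposure around the start of pembrolizumab is something the plan already treats as relevant, since exclusion criterion 3.2.9 bars systemic steroids in the 7 days before first treatment.

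**Working it through.** No design figure is involved, so the check sets the passages side by side.

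**1. Do the rules apply at the same time?** Yes. The Section 5.4.2 list covers the treatment phase. Targeted therapy runs for the 2-week lead-in plus 6 weeks with pembrolizumab, 2 + 6 = 8 weeks, all within that phase.

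**2. Does either exception in 5.4.2 cover the table rows?**

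| Instruction | Force | Immune exception | Physiologic-dose exception |
|---|---|---|---|
| Pyrexia, first-event row | No steroid in the row itself | Not needed | Not needed |
| Pyrexia, complicated and uncontrolled | Recommended | No immune cause stated | No dose given; no PI step |
| Pyrexia, second event | To be considered; prednisone 10 mg is the example | No immune cause stated | Documents do not say whether this is physiologic; no PI step |
| Pyrexia, later events and footnote h | Directive | No immune cause stated | Escalating doses, no stated ceiling; medical monitor consulted only if a taper fails |
| Rash, grade 3 or higher | Directive | Not stated; possible once pembrolizumab has started | Not called physiologic; no PI step for starting the steroid |

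The immune-event steroid guidance in Section 5.4.5.1 does not fill the gap, because it is meant for events judged related to pembrolizumab.

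**3. Where is the conflict sharpest?** In the lead-in. Pembrolizumab begins only after the 2 weeks of targeted therapy (Section 5.3.1), so fever or rash before then cannot be attributed to it, and the immune exception is hardest to invoke.

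**4. Do the passages lead to the same outcome?** No. Section 5.4.2 raises discontinuation. The pyrexia table restarts dabrafenib on recovery, and Table 6-3 restarts study treatment one dose level lower once the rash has settled. A site that withheld steroids under 5.4.2 also could not apply the footnote h trigger as written.

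**5. How often would it arise?** The documents do not say. Section 2.2.2.4 gives pyrexia in 39 of 55 patients on the full-dose combination in the randomized part (39/55 = 0.709, or 71%) and in 88% at that dose in the escalation part. Both count any pyrexia. Steroids enter only for complicated, uncontrolled fever or for repeat events. The figures come from studies without this plan's 8-week limit, and the wild-type cohort receives no dabrafenib. For rash, Section 2.2.3.3 reports grade 3 events in 1% to 18% of patients across trials at the 2 mg trametinib dose. That is an event rate, not a rate of steroid use.

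**6. Could it reach the primary endpoint?** Section 13.1 counts a patient who is unevaluable for response as a non-responder, and stage 1 stops a cohort at 8 of 14 but continues it at 9 of 14, so one patient handled differently could matter at the boundary. Several links are missing, however. Section 5.5 does not list use of a prohibited drug as a reason to leave protocol therapy. Section 5.1 moves a patient who cannot tolerate the combination to pembrolizumab alone, if that is safe. The endpoint itself requires being off targeted therapy after induction, so stopping it early is not failure.

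**The case against.** The strongest reply is that 5.4.2 resolves the matter itself: discontinuation only may be required, the investigator has the final decision on supportive therapy, and other medically necessary drugs are allowed. Section 6.2.3 also permits clinical judgment on skin events. This has weight. A reader might infer that sites cannot possibly comply with both sections; the documents do not support that, because an investigator can rely on this clause. The clause does not remove the inconsistency, though. It names neither steroids nor the toxicity tables, it follows directly on the discontinuation warning, and Section 5.4.1 places drugs prohibited in 5.4.2 outside general investigator discretion. Leaving each investigator to choose also permits the uneven handling described above.

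A second reply is that the two exceptions absorb much of the conflict. Part of this stands. Severe skin reactions appear among the potentially immune-mediated events reported for this triplet in Section 2.2.1.2, so some grade 3 or higher rash during the 6 weeks on pembrolizumab could qualify. Section 5.4.1 refers to Section 7 for the definition of events of clinical interest, and part of Section 7 is not in the text available for review, so the exact scope cannot be checked. Even so, the exception requires a suspected immunologic cause, which Sections 6.2.2 and 6.2.3 do not assert. The physiologic-dose route needs a consultation that neither table asks for when steroids are started.

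Third, the early pyrexia wording is advisory. That is correct; only the later pyrexia rows and the grade 3 or higher rash row are directive.

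**Conclusion.** The inconsistency is real and lies in the operative text. Section 5.4.2 restricts systemic steroids in a way that does not accommodate what the pyrexia table and Table 6-3 call for, and nothing links the sections. It is clearest for events attributed to dabrafenib or trametinib, especially in the lead-in.

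Two stronger readings should be resisted. A reader might take 71% or 88% as the share of patients who would meet the conflict. These are any-pyrexia rates and show only that the underlying event is common with the drugs given to the BRAF-mutant cohort. A reader might also infer that the week-24 result is compromised. An effect is possible, but no passage demonstrates one.

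The conclusion rests on reading 5.4.2 as governing the whole treatment phase, as it states, and on the missing part of Section 7 not extending events of clinical interest to targeted-therapy fever and rash in a way that also supplies the immunologic cause. It should be corrected as a matter of safe and uniform conduct; it is not a flaw in the statistical design.

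**What to change.** Reconcile Section 5.4.2 with the pyrexia table in Section 6.2.2 (one of two tables numbered 6-2, so identify it by title) and with Table 6-3. All three should state the same rule on:

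- whether systemic steroids may be used for toxicity attributed to dabrafenib or trametinib;
- whether Overall PI consultation is needed, and when;
- whether such use leads to discontinuation, and from which agent.

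Add cross-references in both directions, and make sure footnote h can be applied under the agreed rule. Check the pneumonitis table in Section 6.2.12 in the same edit, since it also allows corticosteroids when clinically indicated. Which rule is right is a clinical decision for the sponsor.

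The cost is amendment wording only. Sample size, endpoint and analysis are unaffected. Section 5.4.1 already requires concomitant medications to be recorded on the case report form.
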